# 2.8 Safety analyses

All safety analyses will be on SAF and presented by study treatment actually received (Section 2.2).

If not clarified otherwise, safety summaries will include only data from the on-treatment period except that baseline data may also be summarized where appropriate (e.g. change from baseline summaries). The on-treatment period lasts from the date of first administration of study treatment to 30 days after the date of the last dose date.

# 2.8.1 Adverse events (AEs)

All reported AEs will be coded based on the latest MedDRA version practically possible before database lock and clarified in footnotes of reports.

The number (%) of patients with treatment emergent adverse events (TEAE, defined as events that started after the first dose of study treatment or events that were present prior to start of study treatment but increased in severity during on-treatment period) will be summarized by study treatment and in the following ways:

- by primary system organ class (SOC) and preferred term (PT).
- by primary SOC, PT and maximum severity.
- by Standardized MedDRA Query (SMQ) and PT.
- by SOC and PT for study treatment related adverse events,
- by SOC and PT for serious adverse events (SAE),
- by SOC and PT for TEAE leading to study treatment discontinuation.

A patient with multiple adverse events of same SOC or PT will only be counted once towards the specific SOC or PT and according to the greatest severity reported.

#### **Clinical Trial Safety Disclosure**

Regulatory-required safety disclosure tables will be produced with the final CSR.

For the legal requirements of ClinicalTrials.gov and EudraCT, two required tables on <ontreatment/treatment emergent> adverse events which are not serious adverse events with an incidence greater than 5% and on <on-treatment/treatment emergent> serious adverse events and SAE suspected to be related to study treatment will be provided by system organ class and preferred term on the safety set and for the overall study period.

If for a same patient, several consecutive AEs (irrespective of study treatment causality, seriousness and severity) occurred with the same SOC and PT:

- a single occurrence will be counted if there is  $\leq 1$  day gap between the end date of the preceding AE and the start date of the consecutive AE
- more than one occurrence will be counted if there is > 1 day gap between the end date of the preceding AE and the start date of the consecutive AE

For occurrence, the presence of at least one SAE / SAE suspected to be related to study treatment / non SAE has to be checked in a block e.g., among AE's in  $a \le 1$  day gap block, if at least one SAE is occurring, then one occurrence is calculated for that SAE.

The number of deaths resulting from SAEs suspected to be related to study treatment and SAEs irrespective of study treatment relationship will be provided by SOC and PT.

#### **2.8.1.1** Adverse events of special interest / grouping of AEs

Number (%) of patients with treatment emergent pruritus, diarrhea, hypoglycemia and pancreatitis) will be summarized separately for each event(in total and by the PTs contributing to it) by study treatment. Kaplan-Meier curves for the time (days) from baseline to patient's first incidence of pruritus, diarrhea and hypoglycemia by study treatment will also be provided

separately for each of the three AEs.

Number (%) of patients who experienced following safety events will be presented by study treatment separately.

- liver safety events identified according to protocol section 16.2
- renal safety events identified according to protocol section 16.3

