• To evaluate the relationship of investigational treatment and markers of hepatic inflammation in NASH (ALT and AST) after 48 weeks of treatment	 Change in ALT and AST over time up to Week 48 compared with Baseline
• To evaluate the relationship of investigational treatment and GGT, a marker of cholestasis and oxidative stress after 48 weeks of treatment	Change in GGT over time up to Week 48 compared with Baseline
 To evaluate the safety and tolerability of tropifexor (LJN452) in combination with licogliflozin (LIK066), and each monotherapy treatment, compared to placebo, after 48 weeks of treatment 	 Occurrence of adverse events, serious adverse events, adverse events resulting in discontinuation of study treatment, adverse events of special interest and changes in vital signs and laboratory parameters

Novartis Amended Protocol Version 02 (Clean)	Confidential	Page 63 of 160 Protocol No. CLJN452D12201C

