10.2.3 Adverse events of special interest

10.2.3.1 Pruritus

Pruritus is a common adverse event for the FXR-agonist class of drugs. Events will be captured during the study. Pruritus should be managed according to normal standard of care. If a participant experiences pruritus, an interruption in dosing of study medication can be considered. Although not specific to NASH, guidance for pruritus management can be found in the guidelines of the American Association for the Study of Liver Diseases (AASLD) and the European Association for the Study of the Liver (EASL) for the management of cholestatic pruritus. (Lindor KD, Gershwin ME, Poupon R et al 2009, J Hepatol 2009). Protocol rules outlined in Section 6.2 for Other Treatments must be followed.

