10.2.3.2 Dyslipidemia

Management of dyslipidemia is critical in participants with NASH. Increases in LDL-C and decreases in HDL-C are observed with experimental treatments for NASH including the FXR-agonist class of drugs, such as tropifexor. The participant's cardiovascular risk should be assessed by the investigator. Lipids are monitored by regular laboratory testing during the study. Dyslipidemia should be aggressively managed to achieve appropriate target levels, as recommended by local/ regional guidelines. Interventions, such as diet, exercise, and especially early introduction of lipid-lowering agents (e.g. statins) should be considered. Doses of lipid lowering agents should be adjusted as required to reach appropriate lipid levels.

Confidential

Laboratory abnormalities related to lipids should be reported as an adverse event only if the criteria in Section 10.1 are met. Cardiovascular events would be closely monitored and captured during the study.

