10.2.3.4 Genital infections

In clinical studies with licogliflozin, a small number of participants experienced non-serious, mild genital infections (mainly mycotic) with AEs including balanitis and vulvovaginal infections. This is observed due to dose dependent glucosuria as a consequence of SGLT2 inhibition. All genital infections reported in licogliflozin clinical trials were non-serious with the overall frequency similar to published reports for marketed SGLT2 inhibitors (dapagliflozin, canagliflozin).

Participants with symptomatic genital infection in the 4 weeks before randomization should be excluded. The possibility of genital infections (mainly mycotic like thrush) is described in the clinical study informed consent forms. Participants will be instructed to pay attention to genital hygiene and have appropriate hydration and be warned that severe genital infection may require urgent medical attention (see Section 10.2.3.8, Fournier's gangrene).

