10.2.3.7 Ketoacidosis

Euglycemic ketoacidosis is a rare adverse event reported with SGLT-2 inhibitor class of drugs. Participants are advised to maintain hydration and avoid excessive alcohol consumption. Participants should seek medical attention immediately in case they develop any of the following symptoms: vomiting, dehydration, labored breathing, unusual fruity smell in breath, tachycardia, confusion or disorientation and/or coma. Please note that blood glucose levels may be normal in this condition. Laboratory investigations for ketones, electrolytes and anion gap must be performed immediately. The participant must be hospitalized and managed for ketoacidosis as in normal clinical practice. Study medication should be interrupted and precipitating factors must be identified. Participants are advised to interrupt study medication in situations which can predispose ketoacidosis such as during prolonged fasting due to illness or surgery. If ketoacidosis is confirmed, the event must be reported as an SAE. All tests and procedures related to the diagnosis and treatment of the event should be recorded in the appropriate eCRFs.

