10.2.3.8 Fournier's Gangrene

Fournier's gangrene is a rare adverse event reported with SGLT-2 inhibitor class of drugs. Participants are advised to pay attention to genital hygiene. Participants developing fever with pain or swelling in genital or anal region or any other signs/symptoms of infection of genitalia

Novartis	Confidential	Page 130 of 160
Amended Protocol Version 02 (Clean)		Protocol No. CLJN452D12201C
or perineum must seek medical advice immediately. Prompt treatment (including antibiotics		
and consideration of surgical debridement) should be instituted. Study medication should be		
discontinued. If the diagnosis of Fournier's gangrene is confirmed, the event must be reported		
as an SAE. All tests and procedures rela	ted to the diagnosis a	ind treatment of the event should

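### SAP 2.8.1.1 prespecifies an adverse-event-of-special-interest summary for only four of the eight such events in protocol 10.2.3; dyslipidemia, genital infections, ketoacidosis and Fournier's gangrene have none

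*SAP*

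**What the plan says.** Protocol Section 10.2.3, headed "10.2.3 Adverse events of special interest", has eight subsections, one per event. Pruritus, diarrhea, hypoglycemia and pancreatitis are four of them. The others are "10.2.3.2 Dyslipidemia", "10.2.3.4 Genital infections", "10.2.3.7 Ketoacidosis" and "10.2.3.8 Fournier's Gangrene".

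Protocol Table 2-1 ties the safety objective to an endpoint that includes the occurrence of "adverse events of special interest and changes in vital signs and laboratory parameters". The protocol summary also lists AESIs among the key safety assessments.

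SAP 2.8.1.1 is the only place in either document that specifies an AESI analysis: "Number (%) of patients with treatment emergent pruritus, diarrhea, hypoglycemia and pancreatitis) will be summarized separately". The summary is by study treatment, in total and by the preferred terms that contribute. The section then adds Kaplan-Meier curves for three of the four events, and counts of liver and renal safety events. Protocol 12.5.2.1, which plans the adverse event tables, does not mention AESIs.

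**The concern.** The SAP list covers half of the protocol list. Anyone programming from the SAP would produce AESI tables for four events and none for the other four, although the endpoint in Table 2-1 makes no such distinction.

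The events left out matter for this combination. The protocol links dyslipidemia to the FXR-agonist class, to which tropifexor belongs. It links genital infections to glucosuria from SGLT2 inhibition, and ketoacidosis and Fournier's gangrene to the SGLT2-inhibitor class. A grouped row fixed in advance shows the total number of affected participants per arm. Without one, the reader must assemble the total from scattered preferred terms, or someone must choose the terms after unblinding.

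**Working it through.** No power, alpha or sample-size figure is involved, so the check is a count and a comparison of the two documents.

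**Step 1: compare the lists.** SOC/PT means system organ class and preferred term; SAE means serious adverse event.

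| Event | Protocol | AESI summary in SAP 2.8.1.1 | Other planned output by arm |
|---|---|---|---|
| Pruritus | 10.2.3.1 | Yes | SOC/PT tables |
| Dyslipidemia | 10.2.3.2 | No | SOC/PT tables if recorded as an adverse event; lipid values by visit and shift tables (SAP 2.8.3) |
| Diarrhea | 10.2.3.3 | Yes | SOC/PT tables |
| Genital infections | 10.2.3.4 | No | SOC/PT tables |
| Hypoglycemia | 10.2.3.5 | Yes | SOC/PT tables |
| Pancreatitis | 10.2.3.6 | Yes | SOC/PT and SAE tables |
| Ketoacidosis | 10.2.3.7 | No | SOC/PT and SAE tables |
| Fournier's gangrene | 10.2.3.8 | No | SOC/PT and SAE tables |

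Protocol events: 8. SAP events: 4, all of them in the protocol list. Missing: 8 − 4 = 4.

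**Step 2: look for another named grouping.** SAP 2.8.1 plans a table by SMQ and preferred term but names no SMQ, so it does not guarantee a grouping for any of the four. Protocol 12.5.2.1 mentions a summary of other significant adverse events without saying which events these are. No other part of SAP 2.8 names or groups the four as adverse events.

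**Step 3: find the cause.** The SAP history shows one version, 09-Dec-2019. The protocol's change log, used here only for timing, shows that Amendment 01 (18-Sep-2020) added exactly these four events. SAP 1.1 still describes about 210 patients in three arms without placebo.

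**Step 4: judge the loss event by event.**
- *Ketoacidosis and Fournier's gangrene.* Protocol 10.1.2 has both assessed as serious in every case, so the SAE table shows any that occur. What is missing is completeness, including an explicit zero if none occur.
- *Dyslipidemia.* Lipid values are summarised by visit and arm. Under protocol 10.2.3.2 and 10.1.1 a lipid abnormality becomes an adverse event if, among other criteria, it requires therapy. The protocol encourages lipid-lowering treatment, which can reduce on-treatment differences in mean lipids. Mean values do not count the participants with such events; a grouped row would.
- *Genital infections.* Protocol 10.2.3.4 describes those seen so far as non-serious and names balanitis and vulvovaginal infections, so they are neither likely to reach the SAE table nor confined to one preferred term. The full SOC/PT table has no threshold and would show each term. The public-disclosure table for non-serious events (SAP 2.8.1) is limited to incidence above 5%, by term. Assume that the limit applies within an arm, that each participant contributes one term, and that events spread evenly over k terms. A term is at or below the limit with up to 0.05 × 80 = 4 participants in the licogliflozin arm and 0.05 × 140 = 7 in the combination arm. For k = 2, no term passes with up to 2 × 4 = 8 of 80 or 2 × 7 = 14 of 140 affected (10%). For k = 5 the figures are 5 × 4 = 20 of 80 and 5 × 7 = 35 of 140 (25%). These are ceilings under assumed k, not expected rates; the documents give no incidence.

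**The case against.** The strongest reply is that nothing is hidden. All four events are tabulated by arm in the general adverse event tables. Two of them are always serious and are described in the protocol as rare. Lipids have by-visit summaries and shift tables, and an SMQ table is planned. This stands. A reader might infer that the four events would go unreported or could not be compared between arms, and the documents do not support that. Nor is a formal test lost: SAP safety output is descriptive for all AESIs.

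A second reply is that the SAP is simply old. It matched an earlier protocol, and SAP 1.1 says it may be amended after a protocol amendment. This also stands as an explanation, and it rules out the inference that the sponsor chose to leave these events out. It does not close the gap. The provision is permissive, and no amended SAP is among the documents. The SAP introduction says it implements protocol section 12, whereas the AESI list is in Section 10.2.3, so an update keyed to section 12 could miss it.

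A third is that the Kaplan-Meier curves cover only three events. That is no defect: the protocol requires no time-to-first-event curve for any AESI.

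**Conclusion.** The point holds, with limited consequences. The list in SAP 2.8.1.1 is wrong as written against the current protocol: four of eight AESIs lack the prespecified summary that the other four receive, although AESI occurrence belongs to a secondary safety endpoint. Four of eight counts events; it does not measure lost information. The real loss is mainly for genital infections, then for dyslipidemia recorded as an adverse event, and is small for ketoacidosis and Fournier's gangrene.

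This rests on the SAP supplied being the one in force. If a later version already lists all eight events, the point falls away.

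**What to change.** In SAP 2.8.1.1, replace the four-event list with the eight events of protocol 10.2.3. Define each by a preferred-term list or a named SMQ, fixed before unblinding. Summarise each as number and percentage of participants, in total and by contributing term, for all four arms. Make the change as part of aligning the SAP with the amended protocol. No added Kaplan-Meier curves are needed.

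The cost is SAP wording and four more tables from data already collected.

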#### 2.8.2 Deaths

Patients who died any time during the study will be listed with the date (study day) and reason of death as well as the preferred term, verbatim term, start date (study day) and action taken of SAEs leading to such deaths.

#### 2.8.3 Laboratory data

Summary statistics of values and changes from baseline will be provided by visit (AV2) and by study treatment for laboratory tests listed in Table 2-6. Change from baseline will be summarized for patients with both baseline and post baseline values.

laboratory test group	Parameters	
Hematology	Hemoglobin (Hb), Hematocrit (Hct), Red blood cells (RBC), Mean corpuscular volume (MCV), Platelets, White blood cells (WBC), absolute WBC differential counts ((Neutrophils, Lymphocytes, Monocytes, Eosinophils, Basophils separately)	
General Clinical Chemistry	Sodium, potassium, chloride, bicarbonate, calcium, magnesium, phosphorus, uric acid, haptoglobin	
Liver	ALT, AST, ALP, GGT, creatine kinase (CK), lactate dehydrogenase (LDH), total bilirubin, albumin, total protein	
Renal	BUN, creatinine, estimated glomerular filtration rate (eGFR)	
Urinalysis	Albumin-creatinine ratio (ACR), Protein-creatinine ratio (PCR)	
Coagulation	INR, APTT, Prothrombin Time (PT) and Thrombin Time (TT)	
Lipids and vascular risk	Total cholesterol, HDL-C, LDL-C, VLDL-C, triglycerides, free glycerol and free fatty acids, ApoAI, high sensitivity C-reactive protein (hsCRP)	

 Table 2-6
 Laboratory safety endpoints

Shift tables for normal / abnormal (low and high based on the low/normal/high classifications from central lab) from baseline to the most extreme post-baseline value will be provided.

Number (%) of patients with post-treatment changes in laboratory criteria related to hepatotoxicity or nephrotoxicity criteria (Section 5.3.1) will also be summarized by criteria and by study treatment. In addition, patients meeting a criterion for hepatotoxicity, nephrotoxicity or other notable abnormalities defined in Section 5.3.1 will be listed, including the criteria met as well as the laboratory test name, date (study day) of lab sampling, results and units for that test and related lab tests throughout the study.

Novartis	For business use only	Page 28
SAP		CLJN452D12201C

For summaries of shift, hepatotoxicity/nephrotoxicity events or other notable laboratory abnormalities outlined above, all post-treatment data will be used regardless of last dose date.

# 2.8.4 Other safety data

#### 2.8.4.1 ECG and cardiac imaging data

The PR, QRS, QT, QTcF, and RR intervals will be summarized by visit and by study treatment.

Number (%) of patients shifting from baseline in the overall normal or abnormal ECG abnormality will be presented by visit and by study treatment.

The Fridericia QT correction formula (QTcF) will be used for clinical decisions and for analyses. Notable QTcF values and changes from baseline will be summarized as categorical variable by visit and by study treatment, where a notable value is defined as a QTcF interval of greater than 450 ms and the categories used for the change (increase) in QTcF are:  $\leq$  30 ms, > 30 to  $\leq$  60 ms and > 60 ms.

[figure not shown]
# 2.8.4.2 Vital signs

The value and change from baseline in vital sign parameters (i.e. pulse rate, systolic blood pressure and diastolic pressure) and anthropometric measurements (i.e. body weight, waist circumference and hip circumference) and derivations (BMI, waist:hip ratio) will be summarized by visit and by study treatment.

[figure not shown]
Patients with clinically notable vital signs as defined in Section 5.3.10 will be listed with the abnormality criteria met as well as the specific test name, date (study day) of measurement, results and units for that and related measurements throughout the study.

Descriptive summaries of values and changes from baseline in pre-dose FGF19 and C4 will be presented by visit and by study treatment. The geometric mean and coefficient of variation will also be presented in the summaries for concentration values. The time (hours) elapsed since previous dose of study treatment will also be summarized by visit and by study treatment together in the same output.

For business use only	Page 30 CLJN452D12201C

# 2.14 Interim analysis

Not Applicable.

# 3 Sample size calculation

The sample size of the study is determined based on power consideration for proving superiority of the tropifexor-licogliflozin combination therapy compared to at least one of the monotherapies.

# 3.1 **Power considerations for primary analysis**

No data is currently available for histological responses after licogliflozin or tropifexor monotherapy, neither is there any definitive theory established for complementary or antagonist interactions between the two molecules. Historical studies published so far also suggest unignorable placebo effect ranging from 8% to 18% for different populations and endpoints, which introduces additional uncertainties about the add-on effect size of the tropifexor-licogliflozin combination therapy compared to either monotherapy even under a bliss independence assumption.

Histological Response definition	Time point	Histological study	NASH population with Fibrosis stages	Placebo response rate
Fibrosis	Month 18	REGENERATE	F1 + F2 + F3	10.6%
improvement of 1 stage and no		(2019) Obeticholic acid	F2 + F3	11.9%
worsening in NASH	Week 52	CENTAUR (2018) Cenicriviroc	F1 + F2 + F3	10.4%
	Week 52	ARREST (2018) Aramchol	F1 + F2 + F3	17.5%
	Week 48	STELLAR3 (2019) Selonsertib	F3	13.2%
	Week 48	STELLAR4 (2019) Selonsertib	F4	12.8%
NASH resolution	Month 18	REGENERATE	F1 + F2 + F3	8%
with no worsening in Fibrosis		(2019) Obeticholic acid	F2 + F3	7.9%
	Week 52	GOLDEN (2016) Elafibranor	F0+F1+F2+F3	9%

#### Table 3-1Placebo effects on histological responses

The response rates for the monotherapies are deemed less likely to exceed 30%. For the stepwise gatekeeping testing procedure adopted for primary analysis, total sample size of 210 (70:70:70) is chosen so that there is approximately 80% power for the first hypothesis test (combination vs licogliflozin) if the true add-on effect is 20% for combination therapy.

Table 3-2	Power under different assumptions of mono and combination therapy
	effect sizes

True response rate assumptions		Add-on effect size in 1 st	power of 1-sided hierarchical tests α=0.05		
Licogliflozin	Tropifexor	Combination	test	1 st test	Both tests
30%	30%	38%	8%	25%	12%
23%	23%	33%	10%	38%	22%
30%	30%	44%	14%	53%	34%
30%	30%	47%	17%	67%	52%
23%	30%	41%	18%	75%	34%
20%	20%	40%	20%	84%	75%
25%	25%	45%	20%	80%	69%
30%	30%	50%	20%	79%	67%
30%	30%	51%	21%	82%	72%
23%	30%	46%	23%	89%	60%

Power calculations were performed with simulations (n=100000) implemented in R 3.3.3, where the primary analysis in each simulated study was performed using z-tests of difference in proportions without continuity correction for simplicity.

The dropout rate of the study is anticipated to be around 10%. Because early termination and missing response data will be incorporated into the primary analysis with multiple imputations, no adjustment for early dropouts from study were implemented for the sample size calculations.

